### **Johns Hopkins Bayview Clinic Recruitment:**

We will distribute a recruitment flyer in the heart failure clinic at the Johns Hopkins Bayview Medical Center. Caregivers that respond to the recruitment flyer will be screened for eligibility. If they are eligible, we will contact them by phone to explain study procedures. If interested in participating, we will schedule the caregiver's baseline interview within 10 days of initial contact. During the baseline interview the research assistant will re-explain the study, obtain written consent (if interview is in-person), or e-consent (if the interview is by phone or DoxyMe or Zoom video call).

**Overview of Study Design (Figure 2):** We propose an open label pilot (n=5) with a subsequent single-blind, two group randomized pilot trial to test the feasibility and gauge an initial effect size of the Caregiver-Support intervention to improve QOL. The immediate intervention group (n=20) will receive the intervention during weeks 0-16. The waitlist control group (n=20) will be provided written materials with community resources for caregivers during the first 16 weeks, then they will begin the intervention. Waitlist

## **Heart Failure Center at Ascension St. Agnes Hospital Recruitment:**

We will distribute a recruitment flyer in the heart failure clinic at St. Agnes. Once we find potentially interested participants through self-referral through the recruitment flyer, we will screen the caregiver for eligibility then contact them by phone, zoom, or in person in clinic to explain study procedures. If eligible by screening and interested in participating, we will schedule the caregiver's baseline interview within 10 days of initial contact. During the baseline interview the research assistant will re-explain the study, obtain written consent (if interview is in-person), or e-consent (if the interview is by phone or DoxyMe or Zoom video call).

## **Open Label Phase:**

The first five participants will be enrolled into an open label pilot study, in which they will automatically receive the Caregiver-Support intervention. The participants will be interviewed after program completion to get feedback on the data collection instruments, intervention content including the number of visits and user-friendliness of intervention components (e.g. purpose in life activity), and satisfaction with the overall program process. This feedback will be used to modify the Caregiver-Support intervention for the waitlist control trial that will begin enrollment following the open label phase.

**Randomization:** Within 48 hours of the baseline interview, we will randomize using redcap randomization and communicate the assignment to participants by letter. At that same time, we will inform the nurse interventionist of the new participant. The intervention nurse will contact the participant within one week to schedule the first appointment. The waitlisted group will receive usual care for caregivers for the first 16 weeks, which is normally limited to inclusion in some clinical assessment and teaching during patient visits. Waitlisted participants will receive monthly study postcards to encourage retention. After 16 weeks, they will begin the intervention. The 32- week assessment will measure whether immediate intervention participants continue the strategies on their own and whether they continue to improve on the self-report scales and will measure improvement following the intervention for waitlisted participants.

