## 4. Study Procedures

**Figure 2: Flowchart of Study Design**

control groups are used to first provide an untreated comparison and second to allow wait-listed participants an opportunity to receive the intervention at a later date. This is especially appropriate given that very few services are currently offered to HF caregivers. To account for estimated 20% attrition we will recruit 53 participants.

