**Table 3: Study Visit Timeline for Immediate Intervention Group\***

Format and timing of visits	Key activities
Baseline Data Collection	Sweatpatch application Heartrate Variability Measurement Survey
Sweatpatch Pickup	72 hours post-application, remove sweatpatch and deliver for storage and analysis
Randomization	Mail randomization results
Home Visit Week 1	Assessment Set goals and discuss priorities Remove sweatpatch and deliver for storage and analysis (if not already performed)
Home Visit Week 3	Purpose in Life activity Instrumental Support activity: Benefits Check Up Assess goal attainment and revisit strategies
Phone Check-in Week 4	Review/edit purpose statement Assess goal attainment and strategies to achieve goal
Home Visit Week 6	Social Support Activity Assess goal attainment and strategies to achieve goal Follow-up re: instrumental support
Phone Check-in Week 8	Review/edit purpose statement Assess goal attainment and strategies to achieve goal
Home Visit Week 10	Assess goal attainment and strategies to achieve goal Follow-up re: instrumental and social support
Phone Check-in Week 12	Review/edit purpose statement Assess goal attainment and strategies to achieve goal
Home Visit Week 14	Review of progress, goals and purpose Discuss how caregiver will involve social support in next goals
Data Collection Visit Week 16	Sweatpatch application Heartrate Variability Measurement Survey
Sweatpatch Pickup	72 hours post application
Data Collection Visit Week 32	Sweatpatch application Heartrate Variability Measurement Survey
Sweatpatch Pickup	72 hours post application

\* Waitlist control group will begin intervention at week 16.

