#### Data Management:

Data from screening, intervention sessions, and final data collection will be entered onto forms that the data manager will check for completeness and appropriateness. The data manager will send reports of missing or inappropriate entries to the PI every week for clarification and resolution. As a phase 1 pilot study, a Data Safety and Monitoring Board is not required, however, as part of the P30 PROMOTE Center, a Data Safety and Monitoring Board has been established. Details are provided in the human subjects section.

Fidelity: The fidelity plan is based on the NIH Behavior Change consortium developed by national leaders. We will enhance fidelity through design elements (intervention is distinct and based on theory), training (using an intervention manual), delivery (reminder calls the night before intervention sessions, and measure fidelity through records of home sessions (by date and duration), checklists completed by study team

members and direct observations and discussions concerning intervention engagement to evaluate receipt, and enactment. Ten percent of sessions will be audio taped which will be reviewed by the research coordinator using a priori monitoring checklists developed for this pilot trial. All data collection and intervention interactions will be recorded. Evaluation will include periodic assessments of data quality, participant recruitment, accrual, and retention. Feedback will be provided to each interventionist who will provide case presentations in supervisory sessions. Bi-weekly meetings of the nurse interventionist with the Research Coordinator, the PI, and [name] will assure on-going fidelity to the intervention.

**Study duration and number of study visits required of research participants:** Participation in the study will consist of initial study consent, baseline, 16 and 32-week data collection and 5 study interactions for the intervention. Based on participant preference, the nurse interventionist may also arrange phone calls between visits to assess progress towards goals.

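### Monthly retention postcards go only to the waitlist arm, although the immediate arm has an equally long gap without scheduled contact before the week-32 visit, which could lead to greater or selective loss there.

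*Combined protocol and SAP*

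**What the plan says.** The only retention measure that is specific to one arm is in the Randomization paragraph of Section 4: "Waitlisted participants will receive monthly study postcards to encourage retention". It stands in the text on that arm's first 16 weeks. No end date is given.

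For the immediate arm, "The immediate intervention group (n=20) will receive the intervention during weeks 0-16". Table 3 lists its last nurse session as "Home Visit Week 14". Data collection follows at week 16 and a sweat-patch pickup 72 hours later. The next row is "Data Collection Visit Week 32". The footnote to Table 3 adds that "Waitlist control group will begin intervention at week 16", so the waitlist arm is in contact with the nurse during the weeks when the immediate arm is not.

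The week-32 assessment is meant to show "whether immediate intervention participants continue the strategies on their own" and whether their self-report scores go on improving. It also enters the GEE group-by-time model in Section 7a. Section 7c uses the percentage staying in each arm as one measure of acceptability.

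Section 10 gives both arms $20 at the start, week 16 and week 32, and a tablet. Attrition is a single overall figure: "To account for estimated 20% attrition we will recruit 53 participants".

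**The concern.** The plan bridges one arm's long interval without visits and leaves the other arm's interval of the same length unbridged. Caregivers who have dropped their goals or are struggling may be harder to bring back for week 32. If they are lost, those who remain will look as if they maintained their gains better than the whole arm did.

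Two features of the plan add to this. Section 7 names no method for missing data, and ordinary unweighted GEE is generally valid only when data are missing completely at random. In addition, if one arm is prompted to stay and the other is not, the by-arm retention percentages in Section 7c measure the prompts as well as the acceptability of the intervention.

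**Working it through.** **Plan's own attrition figure.** The target of 53 is the only number based on attrition. From 40 randomized, 40 / (1 − 0.20) = 50 and 40 × 1.20 = 48. Adding the 5 open-label participants to the second gives 48 + 5 = 53, an exact match, but the documents do not say that this is how it was reached. The 20% is not split by arm or by visit, so it says nothing about weeks 16 to 32 in particular.

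**Length of the gaps (Table 3).**
- Immediate arm: week 16 plus 72 hours to week 32 = 16 weeks − 3 days = 109 days, with no retention contact listed.
- Waitlist arm: baseline plus 72 hours to week 16 = 16 weeks − 3 days = 109 days, with monthly postcards.

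**Could another contact fill the immediate arm's gap?** Section 4 says "the nurse interventionist may also arrange phone calls between visits to assess progress towards goals". Those calls are intervention contacts about goals, and Table 3 places them at weeks 4, 8 and 12. The telephone check-ins, text reminders and night-before reminder calls elsewhere in Section 4 are also tied to sessions. None reaches weeks 16 to 32 in this arm.

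**Possible size (assumed inputs).** Let p be the proportion lost in an arm and d the difference in mean change, in SD, between those retained and those lost. The mean among those retained differs from the full-arm mean by p × d. If d is the same in both arms, the between-arm bias is (p_immediate − p_waitlist) × d. The 95% half-width for a standardized difference is 1.96 × √(1/n₁ + 1/n₂). Assumptions: 20 per arm, total loss held at 20%, d from 0.3 to 0.8.

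| Loss, immediate / waitlist | Retained | Half-width (SD) | Between-arm bias (SD) |
|---|---|---|---|
| 20% / 20% | 16 / 16 | 0.69 | 0 |
| 25% / 15% | 15 / 17 | 0.69 | 0.03 to 0.08 |
| 30% / 10% | 14 / 18 | 0.70 | 0.06 to 0.16 |
| 35% / 5% | 13 / 19 | 0.71 | 0.09 to 0.24 |

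Example: (0.35 − 0.05) × 0.8 = 0.24. The bias depends on proportions only, so it is the same with 24 per arm, where the half-widths are 0.63 to 0.64.

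For maintenance within the immediate arm the distortion is p × d: 0.06 to 0.16 SD at 20% loss and 0.105 to 0.28 SD at 35%. The rise from 20% to 35% loss therefore accounts for 0.15 × d, or 0.045 to 0.12 SD.

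**Chance.** With 20 per arm and a true 20% loss in both, the arms would differ by 2 or more participants with probability 0.55, and by 3 or more with probability 0.32. A modest imbalance in this trial could not be attributed to the postcards.

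**The case against.** The strongest reply is that equal gaps need not carry equal risk. Waitlisted caregivers are waiting and have received nothing from the intervention. By week 16 the immediate arm is scheduled for five nurse visits and three phone check-ins. Table 1 expects goal-setting to build rapport and participation, and expects help with instrumental needs possibly to improve retention. Both arms receive the same payments and the tablet. Over 32 weeks each arm has one intervention period and one period without visits. Retention by arm is already to be described, and the monitoring board receives counts of discontinuations with reasons.

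Much of this stands. A reader might infer that loss is likely to be unequal, with the immediate arm worse. The documents do not support that: they give no attrition by arm and no effect of postcards, and Table 1 points, if anything, the other way. A reader might also add further losses in the gap on top of the 20%. Nothing in the plan places that 20% before week 16, so this may count the same loss twice.

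The reply does not supply a retention contact for the immediate arm in weeks 16 to 32. It also does not explain why a procedure already in use should stop at one arm. Describing retention afterwards does not make the retention procedures equal.

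**Conclusion.** The point holds as a minor gap in trial conduct. Postcards are planned for one arm. The other has a 109-day gap with no scheduled contact and no stated retention measure beyond the shared payment at week 32. This could cause greater or selective loss in the immediate arm where maintenance is judged, and it makes the by-arm retention percentages harder to interpret.

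Under the stated assumptions the between-arm bias runs from 0 to 0.24 SD, and its upper end needs an extreme split of 35% against 5%. The zero for equal loss requires those lost to differ from those retained by the same amount in both arms. The direction (maintenance flattered) requires those lost to have done worse. The issue is selection; precision is almost untouched.

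The primary outcome is change from baseline to week 16, measured before this gap begins, so the primary comparison is not affected. By week 32 both arms are due to have been treated, so the between-arm contrast there is no longer treated against untreated.

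**What to change.** Replace the postcard sentence in the Randomization paragraph with: *Monthly study postcards will go to every randomized participant during any period without scheduled study contact (waitlist arm, weeks 0–16; immediate arm, weeks 16–32). The text will be identical and neutral in both arms and will carry no intervention content.* The neutral text matters because week 32 is meant to show strategies continued without prompting.

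To complete it, name week 32 in the by-arm retention summary of Section 7c and state how missing week-32 data will be handled.

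Cost: 3 to 4 postcards for each of 20 caregivers, or about 60 to 80 in all, and one sentence of protocol text. The downside is a small risk that any contact acts as a reminder.

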## **Intervention Delivery Characteristics:**

The intervention delivery characteristics will consist of an assessment-driven, tailored package of interventions delivered by a nurse interventionist. The intervention will be guided by the theory and evidence-based practices that have been successful in our previous work drawing upon clinical approaches such as patient-centered care and motivational interviewing. Every participant receives each component of the intervention (assessment, goal setting, interactive problem-solving, training) but interventionists clinically tailor content to each participant's goals. Nurse interventionists will be trained and equipped with education materials vetted by national organizations leading caregiving research such as the National Alliance for Caregiving, National Council on the Aging (NCOA) and the, American Association for Retired Persons (AARP). We propose an intervention incorporating 5 individualized, nurse-led, home-based or virtual sessions, with telephone check-ins and text reminders, according to participant preference. Baseline, 16 and 32-week data will be collected by interviewers masked to treatment assignment and without interventionist contact. Each design component, related evidence supporting component selection and intervention delivery is described below.

**Table 1 Intervention Components and Evidence Basis for Component Selection**

Intervention Component	Evidence Basis for Component	Intervention Delivery
1) Whole-person physical and psychosocial assessment including personal goals	

- Caregiver physical and psychosocial assessment is suggested by HF guidelines, but not commonly used in practice

- Involving the caregiver in assessment and encouraging them to

	A trained nurse will assess the caregiver using a holistic physical and psychosocial assessment used in previous studies. The nurse will focus on caregiving tasks and factors contributing to a sense of burden.

	
set their own goals is person-centered, builds rapport and increases participation.
	
The nurse will share observations with the caregiver to inform goal-setting.

2) Discussing caregiving in the context of the caregiver's identified 'purpose.' A nurse will lead the caregiver through activities designed to help identify or refine a statement of purpose in life.	
 
- Purpose in life was associated with lower mortality and CVD, stroke, MI, better preventive health behaviors, lower allostatic load
 
- Purpose in life can be improved through intervention and is linked to down-regulation of pro-inflammatory genes
 
	
A trained nurse will lead the caregiver through activities designed to help the caregiver identify and write a statement of purpose in life. For this purpose, a deck of question cards have been developed. The caregiver will choose one or more cards from each of 4 themes: purpose, experience caregiving, caring for yourself and emotions. Comments made will be used to create a summary purpose statement.

3) Co-development of incremental action plans that address personal goals to improve quality of life and reduce fatigue and caregiver burden. A list of goals will be constructed and prioritized. Caregivers will design and work on incremental action steps related to goals, through tailored strategies developed through collaboration with the nurse.	
 
- Incremental action plans based on individually tailored goals, allowing the participant to prioritize their own goals and strategies, increases self-efficacy and encourages participants to use their new skills with other problems.
 
- Studies incorporating this technique have resulted in improved QOL, self-efficacy related to falls, depression and decreased disability.
 
- Goal attainment achieved in 73% of functionally impaired older adults-independent of age, race, gender – higher pain group less likely to achieve goals.
 
	
A list of goals related to addressing fatigue, caregiver burden and perceived threats to QOL will be constructed and prioritized. During the nurse-led sessions, caregivers will work on action steps related to goals in order of priority through tailored strategies developed through collaboration with the nurse.

Instrumental Support refers to the tangible help that others may provide (e.g., help with financial needs, provision of transportation or support with medication management).	
 
- Instrumental support may enhance emotionally supportive interventions
 
- Addressing needs to support instrumental activities of daily living may improve retention from participants
 
- Interventions that provide instrumental support while equipping community members are more sustainable and impactful than providing the support without considering social support/network.
 
	
BenefitsCheckUp is a free, confidential service provided by the National Council on the Aging (NCOA) for people 55 and over and their caregivers. The nurse interventionist will help the caregiver explore the modules which include topics such as medications, healthcare, income assistance etc. Common unaccessed benefits caregivers may be eligible for include: Medicaid, Food bank access, home energy assistance and tax credits. In addition, the nurse will provide support for caregiving challenges such as medication management or communication with providers of multiple chronic conditions.

Social Support	
 
- Perceived social support can be enhanced through interventions
 
- Helping the caregiver identify ways they are already supported may support a sense of perceived support
 
- Setting goals to engage the existing social network may increase self-efficacy for future needs and engagement
 
	
A trained nurse will lead the caregiver through activities to help caregivers connect to their existing family and community to engage these relationships for support in caregiving. The nurse and caregiver will work through these activities during an in-home visit.

----------------	---	--

### **Intervention Protocol:**

The RN will meet with the caregiver in-home or virtually to perform the whole person assessment in which the nurse will focus on caregiving tasks and factors contributing to a sense of burden. In this assessment, the RN and the caregiver identify and prioritize goals, and make plans to achieve those goals. The study will provide the Caregiver-Support Handbook, including evidence-based educational materials, contact information, and a calendar of sessions that the participant keeps for reference. In each session, the RN assesses goal attainment, reinforces strategy use, reviews problem-solving, refines strategies (examples in Table 3 such as Go4Life and AARP materials), and provides education and resources to address future needs. If sessions are held virtually via phone or DoxyMe video call or Zoom video call, no physical activity goals will be pursued as part of this intervention due to the inability to safely assess the participants physical activity readiness.

Following the session, the RN will find additional resources, tailored to each caregiver. In the final session, the RN reviews the participants' strategies and helps to generalize them to other possible challenges or goals. Sessions will be spaced to encourage practicing new strategies independently after developing them together with the nurse. Although this intervention structure has been successful in work by the mentorship team, we will adjust the timing and frequency of study interactions based on feedback in the open label phase. Bi-monthly meetings of the RNs with the Research Coordinator and the PI will ensure smooth communication, address challenges, supervision, and adherence to intervention fidelity.

**Table 2: Exemplar caregiver goals and intervention approaches**

Example Goals	Intervention Approaches
Physical activity: Increase physical activity by 10% or 1 day per week	1) RN will assess current physical activities, weekly duration and intensity. 2) RN will assess safety of physical activity with Physical Activity Readiness assessment with final evaluation by nurse practitioner 3) RN implements NIA Go4Life physical activities, with emphasis on variety, strength training and cardio in a safe environment. 3) RN will assess interest in group activities or engaging social support to increase accountability and help participant get connected.
Stress management: Decrease exposure to stressors, increase use of coping strategies	1) RN will assess stressors with focus on caregiving-related stress 2) RN will work with caregiver to draft a list of caregiving concerns to be addressed at the next visit with the patient's cardiologist 3) Participant will identify coping strategies such as positive self-talk, ways to defuse stressful situations and prevent stress through restorative activities focused on purpose in life.
Rest: Improve nighttime sleep quality	1) RN to assess for duration, quality and sleep hygiene 2) RN will help caregiver identify modifications to sleep environment and bedtime routine 3) RN will assess for daytime fatigue and sleepiness.

